**Table of Abbreviations**

| Abbreviation or Term | Definition/Explanation   |
|----------------------|--|
| CI                   | confidence interval  |
| CSR                  | Clinical Study Report  |
| CTCAE                | Cancer Institute Common Terminology Criteria for Adverse Events  |
| DDT                  | Data Definition Table  |
| eTPO                 | endogenous thrombopoietin  |
| IP                   | investigational product  |
| ITP                  | immune thrombocytopenia  |
| IVRS                 | interactive voice response system: telecommunication technology that is linked to a central computer in real time as an interface to collect and process information.  |
| source data          | information from an original record or a certified copy of the original record containing patient information for use in clinical research. The information may include, but is not limited to, clinical findings, observations, or other activities in a clinical trial necessary for the reconstruction and evaluation of the trial. Source data are contained in source documents (original records or certified copies, ICH Guideline E6). Examples of source data include subject ID, randomization ID, and stratification value. |
| TPO                  | thrombopoietin   |

## 1. Introduction

The purpose of this statistical analysis plan (SAP) is to provide details of the statistical analyses that have been outlined within the protocol for romiplostim Study 20101221 dated 15 January 2014. The scope of this plan includes the interim analysis and the final analyses that are planned and will be executed by the Biostatistics department or designee unless otherwise specified.

## 2. Objectives

### 2.1 Primary

The primary objective of the study is to describe the percentage of time that pediatric subjects with ITP have a platelet response in the first 6 months from the start of treatment with romiplostim.

### 2.2 Secondary

The secondary objectives of the study are:

- To describe the percentage of time that pediatric subjects with ITP have a platelet response over the study duration
- To describe the percentage of time that pediatric subjects with ITP have an increase in platelet count  $\geq 20 \times 10^9/L$  above baseline over the study duration
- To describe the use of rescue ITP medications
- To describe the incidence of antibody formation
- To describe the safety of romiplostim as a long-term treatment in pediatric thrombocytopenic subjects with ITP

### 2.3 Exploratory

The exploratory objectives of the study are:

- To describe the incidence of sustained platelet response
- To describe the incidence of splenectomy
- To describe the subject incidence of romiplostim self-administration

## 3. Study Overview

### 3.1 Study Design

This is a phase 3b single arm, open-label, multicenter study evaluating the percentage of time pediatric subjects with ITP have a response while receiving romiplostim, defined as a platelet count  $\geq 50 \times 10^9/L$  and in the absence of ITP rescue medications in the past 4 weeks. This protocol will provide open-label romiplostim to thrombocytopenic pediatric subjects with ITP diagnosed for at least 6 months and who have received at least 1 prior ITP therapy (excluding romiplostim) or are ineligible for other ITP therapies.

---

The study design consists of a 4-week screening period, up to a 3-year treatment period, an end of treatment (EOT) visit and an end of study (EOS) visit.

Approximately 200 children with ITP will be enrolled into the study and receive weekly romiplostim until they complete the study, discontinue participation in the study for any reason, or the study ends.

The overall study design is described by a study schema at the end of the protocol synopsis section (refer to the study protocol).

### **3.2 Sample Size**

The sample size for this study is governed by the number of pediatric ITP subjects who meet the eligibility requirements during enrollment period. It is estimated that approximately 200 subjects will enroll into this study. The percentage of time achieving platelet response in the first 6 months of treatment period for ITP subjects with romiplostim (both adults and pediatric) is estimated at 74%. The standard deviation of percentage of time is estimated between 30% and 36% based on previous Nplate data. Given the sample size of 200 subjects, the half width of the 95% confidence interval (CI) for the percentage of time achieving platelet response is estimated to be between 4% and 5%.

## **4. Study Endpoints and Covariates**

### **4.1 Study Endpoints**

#### **4.2 Primary Endpoint**

The primary endpoint is the percentage of time with a platelet response, defined as a platelet count of  $\geq 50 \times 10^9/L$  without rescue medication use for ITP in the past 4 weeks, starting from Week 2 in the first 6 months of the treatment period.

A rescue-evaluable weekly platelet count is defined as a weekly platelet count without rescue medication use for ITP in the past 4 weeks.

In the first 6 months of treatment period, a monthly platelet response is defined as a the median of rescue-evaluable platelet counts of  $\geq 50 \times 10^9/L$ .

For each subject, the percentage of time with platelet response during the first 6 months is calculated as the number of monthly platelet response divided by the total number of months. If the monthly platelet response is missing, it will be imputed based on the neighboring monthly platelet response status and rescue medication use in the month. If a monthly platelet response is still missing after imputation, it is considered as no response in this month. Subjects who discontinued the treatment early due to lack of

response (non-responder to romiplostim) before completing 6 months of treatment, the month(s) following their discontinuation of treatment till the 6th month will be imputed as having no monthly platelet response.

The primary endpoint is summarized by descriptive statistics (n, mean, standard deviation, median, Q1 [25th percentile], Q3 [75th percentile], minimum, and maximum) of this percentage of time with platelet response averaging across subjects.

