10.3.2 Analysis of Key Study Endpoints

10.3.2.1 Efficacy Endpoints

The primary endpoint for this study is the percentage of time with platelet response starting from week 2 in the first 6 months of the treatment period. Platelet response is defined as platelet count $\geq 50 \times 10^9/L$ at a scheduled protocol visit. Platelet counts within 4 weeks of a rescue ITP medication will not be deemed as platelet response. The 95% CI will be calculated for the estimated percentage of time.

Summary statistics of platelet counts and responses will be provided at weeks 1 to 8 and then every 4 weeks.

The percentage of time with platelet response starting from week 2 until the EOT period will be summarized with 95% CI.

Product: Romiplostim
Protocol Number: 20101221
Date: 15 August 2014

Page 48 of 69

Missing platelet counts at weeks 12 and 16, and every 4 weeks thereafter will be imputed by using the mean of the 2 closest non-missing platelet counts within ± 1 week before study discontinuation. If still missing after imputation, platelet counts will be considered as non-response.

The proportion of subjects with splenectomy during the study will be summarized for the subjects who entered this study without splenectomy.

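### SAP 11 declares no changes from the protocol, yet SAP 4.2, 4.3 and 7.4 omit the required 95% CIs, leave rescue-window counts out of a monthly median, impute differently and soften the per-protocol sensitivity analysis

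*SAP*

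**What the plan says.** **Protocol 10.3.2.1.** Response is a count of at least 50 × 10⁹/L at a scheduled visit. On rescue: "Platelet counts within 4 weeks of a rescue ITP medication will not be deemed as platelet response". Missing counts at week 12, week 16 and every 4 weeks thereafter "will be imputed by using the mean of the 2 closest non-missing platelet counts within" one week on either side; anything still missing is non-response. On precision: "The 95% CI will be calculated for the estimated percentage of time", and, for the longer-term endpoint, "The percentage of time with platelet response starting from week 2 until the EOT period will be summarized with 95% CI". Protocol 10.1.2.4 commits to a per-protocol sensitivity analysis of the primary endpoint.

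**SAP 4.2.** A monthly response is "defined as a the median of rescue-evaluable platelet counts of" at least 50 × 10⁹/L, where a rescue-evaluable count has no rescue in the preceding 4 weeks. The child's percentage of time "is calculated as the number of monthly platelet response divided by the total number of months". If a month is missing, "it will be imputed based on the neighboring monthly platelet response status and rescue medication use in the month"; if it is still missing, it is non-response. The listed summaries are n, mean, SD, median, quartiles and range.

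**Elsewhere in the SAP.** SAP 4.3 fills weekly counts by last observation carried forward and lists the same summaries. SAP 10.5 says the percentages will be estimated, and repeats that counts within 4 weeks after rescue are not responses. SAP 7.4 says the per-protocol analysis is something that may be explored. SAP 11 states that the protocol-specified analyses are unchanged.

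**The concern.** This is a single-arm, descriptive study. With no control group and no test, the primary percentage and its interval are the main efficacy result, so the scoring rule largely determines what is reported.

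A reader who relies on SAP 11 would not learn that the scoring unit, the rescue handling, the imputation and the status of the sensitivity analysis differ from the protocol. Nor would that reader see that the required interval is not among the planned outputs.

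The rescue handling matters most for interpretation. The endpoint is meant to count time in response without recent rescue. Under SAP 4.2, a month that includes weeks which cannot be responses by definition can still be credited as a full month of response.

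**Working it through.** **1. The plan's own precision figure.** Inputs from Protocol 10.2 and SAP 3.2: n = 200, SD 30% to 36%, and a stated half-width of 4% to 5%. Half-width = 1.96 × SD / √n.
- SD 30: 1.96 × 30 / √200 = 4.16 points.
- SD 36: 1.96 × 36 / √200 = 4.99 points.

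The stated range is reproduced. SAP 3.2 justifies the sample size by "the half width of the 95% confidence interval (CI) for the percentage of time achieving platelet response", but apart from the abbreviation list this is the only place where the SAP mentions a CI. SAP 4.2, 4.3, 5, 10.1 and 10.5 plan none.

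**2. The two plans side by side.**

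| Item | Protocol | SAP |
|---|---|---|
| Unit | Count at a scheduled visit; no formula for percentage of time | Month, by median (4.2) |
| Rescue-window counts | Not responses | Left out of the median (4.2); not responses (10.5) |
| Imputation, primary | Mean of 2 closest counts within ±1 week, at weeks 12, 16 and every 4 weeks thereafter only | Neighbouring months and rescue use in the month |
| Still missing, primary | Non-response | Non-response |
| Imputation, to end of treatment | No carry-forward rule | Last observation carried forward (4.3) |
| 95% CI, both percentage-of-time-in-response endpoints | Required | Not planned |
| Per-protocol sensitivity analysis | Committed | Optional (7.4) |

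SAP 1 cites the protocol of 15 January 2014. The change lists of Amendments 1 and 2 show no edit to Section 10, and the supplement for the EU, Switzerland and Turkey does not alter 10.3.2.1. Version drift therefore does not explain the differences.

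**3. Direction of the rescue rule.** Hold the monthly median fixed. Scoring a rescue-window count as non-response puts it at the bottom of the month's ordered counts, and adding values at the bottom cannot raise a median. Leaving such counts out can therefore only keep or raise a month's score. An enumeration of 4,288 month patterns found no exception.

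**4. Size for one child (illustration, not from the documents).** Assume weekly counts in weeks 2 to 24: 3 in month 1 and 4 in each of months 2 to 6, so 3 + 5 × 4 = 23. Assume one rescue affecting 4 consecutive counts, which can start at weeks 2 to 21 (20 placements).
- *All other counts at or above 50.* By week: 19/23 = 82.6%. SAP: 6/6 = 100% in 14 placements, a gap of 17.4 points. In the other 6 one month has no evaluable count. The score is then 5/6 = 83.3% if that month is imputed as non-response (gap 0.7) or 100% if as response.
- *One low count in the week before the window* (starts 3 to 21, 19 placements). By week: 18/23 = 78.3%. With an empty month as non-response, the SAP gives 100% in 9 (gap 21.7) and 83.3% in 10 (gap 5.1; 83.33 − 78.26).

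**5. The median rule without rescue moves scores either way.** The fewest responding weeks that guarantee 100% are 2 + 5 × 3 = 17, or 17/23 = 73.9%. One responding week in every month, 6/23 = 26.1%, can score 0%. For a child on 4-weekly counts the monthly median is the single count, so the rule matters only in months with several counts.

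**6. Why a visit-based score needs a stated denominator.** Protocol 6.3 and Table 2 footnote d move stable children to 4-weekly counts. Take a child below 50 in weeks 2 to 5 and at or above 50 afterwards, counted weekly to week 9 and then at weeks 12, 16, 20 and 24. By visit this is 8/12 = 66.7%; by week it is 19/23 = 82.6%.

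**The case against.** **The monthly unit is an elaboration.** This stands. The protocol defines response but not how percentage of time is computed. A reader might infer that a monthly unit in itself contradicts the protocol; the documents do not support that. It has to be declared, not abandoned.

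**The imputation conflict is narrower than it looks.** This also stands. The protocol rule covers only week 12, week 16 and every 4 weeks thereafter, and may have been written for the by-visit summary. The final fallback for the primary endpoint is identical. It would also go too far to say that the neighbour rule is certainly deferred to the Data Definition Table: in SAP 9.3 that sentence follows one about imputed dates, and its reach is unclear.

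**The CI is not deleted, only unlisted.** The SAP says that it details the protocol's analyses, and n, mean and SD allow a reader to compute the interval. That limits the harm. An analysis plan should still list the one measure of precision that the protocol requires.

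**Leaving counts out also keeps them from being called responses.** Protocol 2.4 describes the earlier paediatric trial in those terms. That is a fair reading of each count, but it does not answer the point about the month, which is still credited in full.

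**The illustration is unusual and the effect may be small.** Rescue is allowed mainly for low counts or bleeding, so a child otherwise above 50 is atypical. In the earlier trial 2 of 17 romiplostim children (11.8%) received rescue over 12 weeks. At one window each, 17.4 × 0.118 is about 2.1 points and 21.7 × 0.118 about 2.6, both below the CI half-width. With 17 children, a shorter period and possible repeat rescue, this is an indication and not a bound.

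**Conclusion.** SAP 11 is wrong as written. Two required CIs are not planned, rescue-window counts are left out of the month's score, the imputation rules differ, and a committed sensitivity analysis has become optional. These are textual findings and need no assumption.

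The sizes in steps 4 and 5 rest on the assumed weekly grid and a four-count window. With the monthly rule held fixed, the rescue handling can only favour the estimate, by up to 17.4 or 21.7 points against weekly scoring for the children illustrated.

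A reader might infer that the trial's primary mean is inflated by a comparable amount, or that the SAP's scoring as a whole is biased upwards. The documents support neither: the cohort effect cannot be bounded from them, and the median rule alone can lower a score as well as raise it. The point merits correction but does not undermine the design.

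**What to change.** 1. Add the 95% CI of the mean to SAP 4.2, to percentage of time in response until end of treatment in SAP 4.3, and to SAP 10.5.
2. Restore the firm commitment to the per-protocol sensitivity analysis in SAP 7.4.
3. Choose one scoring rule:
   - (a) score by scheduled visit as in Protocol 10.3.2.1, with rescue-window counts as non-response and a stated denominator that does not treat the unscheduled weeks of children on 4-weekly counts as missing; or
   - (b) keep the monthly median, declare and justify it in SAP 11 together with its rescue handling and imputation rule, and add the visit-level version, with rescue-window counts as non-response, as a sensitivity analysis.
4. List in SAP 11 every departure that remains: the scoring unit, the rescue handling, and the imputation rules of 4.2 and 4.3.

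Scoring rescue-window counts as non-response inside the monthly median should not be required. That hybrid is in neither document and can overshoot: for the child in step 4 whose other counts are all at or above 50, with even splits as non-response, it gives 4/6 = 66.7% in 5 of 20 placements against 82.6% by week.

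The cost is SAP wording and one extra derivation, with no new data. The estimate may be slightly less favourable for children who received rescue.

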#### **11. Changes From Protocol-specified Analyses**

There are no changes to the protocol-specified analyses.

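### For children who stop for reasons other than non-response, SAP 4.2 lets later months be filled as response or dropped; Protocol 10.3.2.1 scores them as non-response, yet SAP 11 declares no change

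*SAP*

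**What the plan says.** SAP 4.2 works by month. It states that "a monthly platelet response is defined as a the median of rescue-evaluable platelet counts" at or above 50 x 10^9/L, and each child's percentage is "calculated as the number of monthly platelet response divided by the total number of months". Missing months are handled in this order:

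1. A missing monthly response is filled first: "it will be imputed based on the neighboring monthly platelet response status and rescue medication use in the month".
2. The catch-all follows: "If a monthly platelet response is still missing after imputation, it is considered as no response in this month".
3. A separate sentence covers one group of early stoppers. For those who stop for lack of "response (non-responder to romiplostim) before completing 6 months of treatment, the month(s) following their discontinuation of treatment till the" sixth are scored as no response.

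Protocol 10.3.2.1 works by visit. Response is a count of at least 50 x 10^9/L at a scheduled visit. A missing count at weeks 12, 16 and "every 4 weeks thereafter will be imputed by using the mean of the 2 closest non-missing platelet counts within" one week either side, before study discontinuation. Then: "If still missing after imputation, platelet counts will be considered as non-response". The reason for leaving plays no part.

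SAP 11 states: "There are no changes to the protocol-specified analyses". SAP 9.3 leaves the imputation algorithm to the Data Definition Table.

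**The concern.** Children can stop for reasons other than non-response: Protocol 8.2.1 lists safety concerns, subject request and loss to follow-up, among others. SAP 4.2 has no rule of its own for their later months. Two outcomes are open.

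- **Filled.** The neighbour step comes before the catch-all and states no cut-off at discontinuation, so an unobserved month next to a month of response can be scored as response.
- **Dropped.** SAP 6 ends the treatment period one week after the last dose. If the six-month window is read with that definition, later months leave the denominator.

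Neither gives a child a lower score than counting those months as non-response. Filling gives a higher score when the last observed month was a response; dropping does so when any observed month was. The choice affects the primary endpoint of a single-arm study, and nothing in the SAP tells a reader which version was computed or that the method departs from the protocol.

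**Working it through.** **Planned precision.** Protocol 10.2 and SAP 3.2 give n = 200 and an SD of 30% to 36%. Half-width = 1.96 x SD / sqrt(200):

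- SD 30: 1.96 x 30 / 14.14 = 4.16 points
- SD 36: 1.96 x 36 / 14.14 = 4.99 points

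This reproduces the stated 4% to 5%.

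**Does the text leave the gap open?** Two features suggest that it does. If the catch-all already scored every month after stopping as no response, the separate sentence on non-responders would have little to do. And SAP 4.3 confines its carry-forward for the secondary endpoints to counts in the treatment period, whereas SAP 4.2 puts no such limit on its fill.

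**One child.** Response in month 2 only; leaves after month 2 for a reason other than non-response; no later count used.

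- Later months scored as no response: 1/6 = 17%
- One adjacent month filled: 2/6 = 33%
- Later months dropped: 1/2 = 50%

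An end-of-study (EOS) count can change this. Protocol 7.8 places it four weeks after the last dose, and Protocol 8.1 asks early withdrawers to attend. With 28-day months (an assumption), a last dose on days 29 to 56 puts the count on days 57 to 84, which is month 3.

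- Count used and below 50: 1/6 = 17% with or without filling; 1/2 = 50% if months are dropped.
- Count used, at least 50 and rescue-evaluable: 2/6 = 33% without filling; 3/6 = 50% with one month filled.

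**Trial mean.** The inputs below are assumptions; the documents do not give them.

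- d = share leaving for other reasons: 3% or 10% (6 or 20 of 200)
- m = last month before leaving: 2, 3 or 4
- Response by month: 40, 70, 80, 84, 85, 85%. The mean is 444/6 = 74%, chosen to match the planning value.
- Leavers follow this profile up to exit, and no EOS count is used.

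Let r be the mean response over months 1 to m, and q the response in month m. Entries are percentage points for d = 3% / d = 10%.

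| m | r | q | One month filled: d x q/6 | Months dropped: d x r x (1 - m/6) |
|---|---|---|---|---|
| 2 | 55.0 | 70 | +0.35 / +1.17 | +1.10 / +3.67 |
| 3 | 63.3 | 80 | +0.40 / +1.33 | +0.95 / +3.17 |
| 4 | 68.5 | 84 | +0.42 / +1.40 | +0.69 / +2.28 |

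Both columns are shifts relative to scoring unobserved months as no response. An EOS count, where obtained and used, would narrow them.

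The same inputs can be compared with the value had the leavers stayed (74%):

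| m | Unobserved as no response: d x (r x m/6 - 74) | Months dropped: d x (r - 74) |
|---|---|---|
| 2 | -1.67 / -5.57 | -0.57 / -1.90 |
| 3 | -1.27 / -4.23 | -0.32 / -1.07 |
| 4 | -0.85 / -2.83 | -0.17 / -0.55 |

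**The case against.** The strongest reply is that months after stopping are not in the window. The endpoint is tied to the treatment period, SAP 6 ends that period one week after the last dose, and SAP 3.1 describes response while receiving romiplostim. On that reading nothing is filled, and the non-responder sentence is a deliberate exception that scores informative dropout as failure. The reading is coherent, and it is why filling is put here as a possibility. It does not remove the point: dropped months also depart from the protocol's rule and, under the assumptions above, shift the mean further than one filled month.

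Other replies stand in part.

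- Filling also depends on rescue use in the month. Protocol 7.4 ends rescue recording at the end-of-treatment or EOS visit, so a later month might stay missing and fall to the catch-all. The SAP does not say whether absent rescue data bar a fill.
- A neighbour might be needed on both sides, and the Data Definition Table may set limits. Neither is stated in the SAP.
- The protocol's rule names only weeks 12, 16 and every fourth week after, refers to study rather than treatment discontinuation, and defines no monthly score. The 1/6 above applies its principle; it is not a figure from the protocol.
- Scoring unobserved time as failure is itself a choice of estimand. Against the value had the children stayed, the mean with one month filled is still about 0.4 to 4.4 points low (0.85 - 0.42 to 5.57 - 1.17). The shifts are upward relative to the protocol's rule, not proof of overstatement against the truth.

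SAP 1 cites the protocol of 15 January 2014. That does not explain the mismatch, because neither amendment summary lists a change to section 10.

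**Conclusion.** The point holds as a gap in SAP 4.2 and an undeclared departure from Protocol 10.3.2.1. The departure needs no dropout assumption: a monthly median with neighbour filling is not a visit count with a one-week window. The size does need assumptions. With 3% to 10% leaving for other reasons after month 2 to 4, the mean is about 0.35 to 1.4 points higher with one month filled, or 0.7 to 3.7 points higher if months are dropped, against a planned half-width of 4.2 to 5.0. The study is descriptive, so no decision threshold moves. It should be fixed, with medium confidence about which reading was intended.

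Three stronger readings are tempting and not supported.

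- A reader might infer that the SAP does credit off-drug months. It can, but dropping them is also a fair reading.
- A reader might infer that the fill chains to month 6, which would give the child above 5/6 = 83%. The SAP neither prescribes nor bars chaining.
- A reader might infer that a child who never responded on drug gains credit after splenectomy. Protocol 6.7 allows splenectomy when treatment is ineffective, and such a child may well count as stopping for lack of response under SAP 4.2. That case rests on a narrow reading and is not part of this point.

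**What to change.** In SAP 4.2:

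- State the denominator as week 2 to the end of month 6 for every dosed child, and name the closing week. SAP 4.4 takes 24 weeks as six months for sustained response; the primary endpoint names no week.
- Limit neighbour filling to gaps before discontinuation.
- Use observed rescue-evaluable counts, and score unobserved months after discontinuation for any reason as no response, following the protocol's rule.
- Report the on-treatment denominator as a sensitivity analysis, since the design describes response on drug.

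In SAP 11, list the monthly-median and neighbour-fill method as a change from the protocol.

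The cost is a few sentences and a little programming. The estimate becomes more conservative: about 0.9 to 5.6 points below the value had the leavers stayed, under the same assumptions, against 0.2 to 1.9 points below if months are dropped. The sensitivity analysis is there to show that difference.

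Separately, Protocol 3.1.2 and 6.2.3 word the non-responder platelet threshold differently and must be reconciled; this point does not rest on it.

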7.1 Schedule of Assessments

The Schedule of Assessments is found in [Table 2](#) below.

Table 2. Schedule of Assessments

Procedures	Screening	In Clinic Dosing Period ^a	Romiplostim Treatment Period (up to 36-months) ^b			End Of Treatment Visit	End of Study Visit
	- 4 Weeks	Week 1 to Week 8	Weekly	Every 4 Weeks	Every 12 Weeks		
Informed consent	X						
Confirmation of primary ITP diagnosis	X						
ITP/medical history	X						
Physical exam	X				X	X	
Vital signs	X				X	X	
Weight	X				X		
Central lab CBC with differential	X	X ^c		X ^b		X	
Central lab blood (serum) chemistry	X				X	X	
Local lab platelet counts	X	X	X ^{b,d}			X	X
Local lab peripheral blood smear		X ^c		X ^b		X	
Pregnancy test	X				X ^f	X ^f	
Concomitant /rescue medications	X	X	X	X	X	X	X
Adverse event reporting		X	X	X	X	X	
Serious adverse events	X	X	X	X	X	X	X
Antibody sample ^e		Day 1 (before first dose)			W12, W52 and every 24 weeks thereafter	X	
Romiplostim dosing		X	X				

ITP = immune thrombocytopenia; CBC = complete blood counts

- ^a Week 1 to Week 8. All subjects will return to the clinic for weekly dosing of romiplostim, platelet counts by a local laboratory, recording of concomitant/rescue medications, and adverse event reporting.
- ^b Subjects who complete 6 months of sustained platelet response (platelet count $\geq 50 \times 10^9/L$ in the absence of romiplostim or any ITP medications) will have assessments every 12 weeks for the duration of the 36-month treatment period.
- ^c Central CBC with differential and local lab peripheral blood smears are to be performed every 4 weeks, including pre-dose at week 1. Screening laboratory studies may be used in lieu of the pre-treatment day 1 week 1 laboratory tests if performed within 10 days prior to the first dose. Bone marrow biopsy suggested if abnormalities detected.
- ^d For subjects who establish a stable dose of romiplostim and are self-administering, have the injection administered by a caregiver, or meet this criterion but still prefer to come to the clinic for romiplostim administration, platelet counts will be monitored every 4 weeks.
- ^e For subjects who test positive for antibodies, see [Section 7.1.3](#). Antibody sampling during romiplostim treatment is only conducted if subject is receiving study drug.
- ^f Local lab urine or serum pregnancy test for female subjects of child-bearing potential (defined as having first menses)

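### SAP 4.2 checks for rescue only within a missing month, so a month masked by rescue late in the previous month can be imputed as a platelet response

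*SAP*

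**What the plan says.** The primary endpoint is the percentage of time in platelet response over the first 6 months, without rescue in the past 4 weeks. SAP 4.2 builds it in steps:

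- Evaluable counts: "A rescue-evaluable weekly platelet count is defined as a weekly platelet count without rescue medication use for ITP in the past 4 weeks".
- Monthly status: "a monthly platelet response is defined as a the median of rescue-evaluable platelet counts of" at least 50 × 10⁹/L.
- Score per child: "the number of monthly platelet response divided by the total number of months".
- Missing month: "it will be imputed based on the neighboring monthly platelet response status and rescue medication use in the month".
- Fallback: "If a monthly platelet response is still missing after imputation, it is considered as no response in this month".

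Protocol 10.3.2.1 treats counts after rescue directly: "Platelet counts within 4 weeks of a rescue ITP medication will not be deemed as platelet response". SAP 10.5 says the same, and the SAP 6 definition of platelet response agrees. For counts that stay missing, the protocol adds: "If still missing after imputation, platelet counts will be considered as non-response". SAP 11 declares no changes from the protocol's analyses.

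Count frequency also matters. Under protocol Table 2, footnote d, once a child is on a stable dose and self-administering (or eligible to), "platelet counts will be monitored every 4 weeks".

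**The concern.** The exclusion window after rescue lasts 4 weeks and so runs into the following month. The rescue check in the missing-month rule does not. If rescue is given late in one month, every count in the next month can fall inside the window. That next month then has no evaluable count and no median. The missing-month rule is the only SAP 4.2 rule that fits it while the child stays on treatment. The month shows no rescue of its own, so its neighbours' status decides.

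The counts in such a month were obtained, and the protocol already classes them as not responses. Treating them as missing opens a route by which they become responses. The no-response fallback does not close it, because it applies only to months that neighbour imputation leaves unresolved. Compared with the protocol rule, the route can add response months but cannot remove any, and it acts only on children who needed rescue.

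**Working it through.** **Planned precision.** Inputs from SAP 3.2: N = 200, SD 30% to 36%, 95% confidence. Half-width = 1.96 × SD / √200.

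- SD 30: 4.16 points
- SD 36: 4.99 points

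This reproduces the stated 4% to 5%.

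**When is a whole month masked by rescue in the month before?** Assume 28-day months (SAP 4.4 likewise equates 6 months with 24 weeks), a single rescue on day r of one month, and counts masked up to and including 28 days after rescue. A count on day c of the next month comes 28 + c − r days after rescue, so it is masked when r ≥ c. The last count of the next month decides whether the whole month is masked.

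| Count schedule | Last count (c) | Rescue days that mask the whole next month |
|---|---|---|
| Weekly, days 1, 8, 15, 22 | 22 | 7 of 28 |
| 4-weekly, count on day 22 | 22 | 7 of 28 |
| 4-weekly, count on day 1 | 1 | 28 of 28 |

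If the 28th day after rescue is not itself masked, the weekly figure is 6 of 28. With calendar months and weekly counts, it is 0 to 5 rescue days per month. The position of the 4-weekly count is not settled by the documents. Protocol 10.3.2.1 names weeks 12 and 16. Week 12 starts on study day 78, which is day 22 of month 3 (78 − 56), and gives 7 of 28. Counts at weeks 1, 5, 9 and so on would give 28 of 28.

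**One child, weekly counts, rescue on study day 50 (day 22 of month 2).** Month 3 counts fall on days 57, 64, 71 and 78, that is 7 to 28 days after rescue, so all are masked. Months 1, 4, 5 and 6 respond. The example counts are illustrative.

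| Month 2 counts | Month 2 status | Month 3 imputed: both neighbours must respond | Month 3 imputed: either neighbour suffices | Month 3 scored as no response |
|---|---|---|---|---|
| 80, 80, 70, 15 | response | 6/6 = 100% | 6/6 = 100% | 5/6 = 83.3% |
| 40, 30, 20, 15 | no response | 4/6 = 66.7% | 5/6 = 83.3% | 4/6 = 66.7% |

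In the first row, month 2 is a response whether or not the day-50 count is included: the median is 80 without it and 75 with it.

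**Effect on the group mean.** One month is 100/6 = 16.7 points for a child. If a share f of children have one such credited month, the mean rises by f × 16.7 points. The documents do not give f, so these values are assumptions:

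- f = 1%: 0.17 points
- f = 3%: 0.50 points
- f = 5.9%: 0.98 points
- f = 11.8%: 1.97 points

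The last value takes the rescue rate of the earlier 12-week pediatric study (2 of 17, protocol 2.4) and supposes that every rescued child has one credited month. To move the mean by the planned half-width would take 4.16/16.7 × 200 ≈ 50 to 4.99/16.7 × 200 ≈ 60 of the 200 children.

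**The case against.** The strongest reply is that the SAP never says a masked month becomes a response. It names two inputs to the imputation but no decision rule, and SAP 9.3 leaves the imputation algorithm to the Data Definition Table, which could close the gap. Even calling a masked month missing is an inference from the median definition. This stands as a limit on the claim: the text permits the outcome but does not require it. It does not remove the problem. SAP 4.2 itself names the rescue check, and a programmer following it literally would look only inside the month.

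A reader might infer that rescue therefore costs a child nothing on the primary endpoint. The documents do not support that. The rescue month is itself a neighbour, and rescue is permitted when counts are low (protocol 6.4), so that month may be a non-response and the imputation may follow it. Under weekly counts, rescue before about the last week of a month leaves evaluable counts in the next month, and their median decides. A rescue course that continues into the next month is caught by the check as written.

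A reader might also infer that children counted every 4 weeks are always masked. That holds only if the count falls on the first day of the month. An effect as large as 4.2 points (25% × 16.7) would need a quarter of all children to be rescued, every next month masked and every neighbour responding. Nothing in the documents supports that combination.

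Finally, the study is descriptive, with no hypothesis test, and rescue use is reported separately. That limits the consequence but does not justify a primary endpoint that can count a month against its own definition.

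**Conclusion.** The point holds as a gap with a known direction. The rescue check in SAP 4.2 is shorter than the endpoint's 4-week look-back, so a month fully masked by rescue late in the previous month can be credited as response. That would conflict with protocol 10.3.2.1, SAP 6 and SAP 10.5, while SAP 11 declares no departure. Each credited month is worth 16.7 points for the child (100% against 83.3%). The likely effect on the mean is modest: about 0.2 to 2.0 points if 1% to 11.8% of children have one such month, which is below the planned half-width. This rests on the assumed share of children, 28-day months, single-administration rescue and responding neighbours. The planned sample size and precision are unaffected. Because the error can only raise the primary percentage and is cheap to remove, it should be corrected before database lock.

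**What to change.** In SAP 4.2:

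1. Score as no response any month in which counts were obtained but none is rescue-evaluable because of rescue in the past 4 weeks.
2. Limit neighbour imputation to months with no count obtained and no rescue in that month or in the 4 weeks before it. A month with no count but with such rescue is no response.
3. State the neighbour rule, for example response only if both neighbouring months respond, and say what applies to months 1 and 6, which have only one neighbour inside the 6-month window.

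The Data Definition Table should then follow this text. The cost is a few sentences and a small programming change. The primary percentage may become slightly less favourable.
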